Strong Point of Inspiratory Muscle Training for Kidney and Immune Functions, and Quality of Life of Chronic Kidney Disease Patients on Hemodialysis

NCT05241652

May 1st, 2022

Study Protocol

This study included patients diagnosed with end-stage CKD who received HD twice a week for more than three months in the Hemodialysis Service. The inclusion criteria were: age 45–54 years, can perform respiratory muscle training (RMT) procedures, have a MIP (Maximal Inspiratory Pressure) value of less than 70% of the predicted measurement results using the micro respiratory pressure meter (RPM) tool, hemoglobin level greater than 8 g/dL, ability to understand oral and written instructions, cooperative and willing to participate in the research, and able to do exercises after signing an informed consent form. The RMT used is Inspiratory muscle training (IMT). The exclusion criteria were: patients with obstructive lung disease, pleural effusion, cardiomegaly, heart failure, coronary heart disease, history of pneumothorax, history of thoracic or abdominal surgery in the last six months, disturbances related to eardrum damage, have received inspiratory and expiratory muscle training in the past six months, and blood pressure >180/110 mmHg or <80/60 mmHg. Subjects are divided into two groups: control and intervention.

We examined the levels of urea, creatinine, and IL-6 (prior to HD) and performed an interview using the KDQOL-SFTM v1.3 questionnaire before the IMT exercise program is conducted. For 12 weeks, the intervention group was assigned an IMT exercise program that included inspiratory muscle strengthening exercises thrice a week at a 50% MIP intensity, five sets per time, ten breathing repetitions per set, for an estimated duration of 20 minutes each using Threshold IMT. The control group received IMT exercise with an intensity of 10% MIP for 12 weeks.

A re-examination of the urea, creatinine, IL-6 levels, and re-administration of the KDQOL HD-SFTM v1.3 questionnaire was performed at the end of the IMT exercise program (after 12 weeks).

Serum urea and creatinine levels were used to measure kidney function. IL-6 levels were used to measure immune function. Inspiratory muscle training included specific exercises to improve ventilation through coordination, endurance, and respiratory strength of the inspiratory muscles. IMT measurements were performed using the Threshold IMT tool. Measurement of MIP was conducted using Micro RPM prior to inspiratory muscle strengthening exercise.

The KDQOL-SFTM v1.3 questionnaire was used to assess quality of life. This questionnaire consists of a physical component summary (PCS), mental component summary (MCS), and kidney disease component summary (KDCS).

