**NCT05241652**

**May 1st, 2022**

**Statistical Analysis Plan (SAP)**

Shapiro-Wilk test will be used to determine the normality of the variables. To compare the two groups, we will use the Unpaired T-test for normally distributed data or the Mann Whitney test for non-normally distributed data. To compare categorical data, we will use the Fisher's test. Paired T-test will be used to compare mean differences before and after intervention for normally distributed data. Wilcoxon's test will be used for non-normally distributed data. The collected data will be analyzed using SPSS version 25.0 for Windows at a statistical significance level (p) of <0.05.

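### No random or concealed allocation is described, and the groups are compared without baseline adjustment, so a baseline difference can be partly read as a training effect

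*Protocol*

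**What the plan says.** The Study Protocol gives group formation one sentence: "Subjects are divided into two groups: control and intervention". It then describes the two programmes. The intervention group trains "thrice a week at a 50% MIP intensity, five sets per time, ten breathing repetitions per set", and for the comparator "The control group received IMT exercise with an intensity of 10% MIP for 12 weeks". Nothing is said about a random sequence, an allocation ratio, stratification, concealment, or who assigns patients. Entry criteria for both arms include being "cooperative and willing to participate in the research, and able to do exercises".

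The SAP states, for the between-group comparison, that "we will use the Unpaired T-test for normally distributed data or the Mann Whitney test for non-normally distributed data". For other data, "To compare categorical data, we will use the Fisher's test". Within groups, "Paired T-test will be used to compare mean differences before and after intervention for normally distributed data", with Wilcoxon's test as the non-normal alternative. The SAP names no covariate, no regression model and no rule for baseline imbalance. It does not say whether the two-sample test is applied to week-12 values or to changes from baseline.

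The protocol has urea, creatinine, IL-6 and the KDQOL measured before training and again after 12 weeks, so a baseline value exists for every outcome.

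**The concern.** An unadjusted two-sample test isolates the effect of training only if group membership is independent of prognosis. Random, concealed allocation secures that independence, and chance imbalance is then already covered by the 5% level. A systematic difference between the arms is not.

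Nothing in the text rules out such a difference. The two arms ask for very different effort (50% against 10% MIP). A team could choose which patient goes where and still comply with every sentence of the protocol. The SAP then uses none of the baseline values that could reduce the consequence. Every between-group conclusion, on kidney function, IL-6 and quality of life, passes through this step.

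**Working it through.** **Stated figures.** The documents give no sample size, SD, effect size or allocation ratio, so there is no figure of theirs to reproduce. What follows is an illustration.

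**Inputs.**
- From the documents: significance level 0.05 (taken as two-sided, which the SAP does not state); baseline and 12-week measurement of each outcome; an unadjusted unpaired t-test.
- Assumed: no true training effect; systematic baseline gap g = 0.3 or 0.5 SD; baseline to week-12 correlation ρ = 0.5 or 0.7; n = 20, 30 or 40 per arm; gap shrinking to ρ × g by week 12; unit SD at both times.

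**Formulas.**
- Week-12 values: standardised bias d = ρ × g.
- Changes: mean bias = −(1 − ρ) × g and SD of change = √(2(1 − ρ)), so |d| = g × √((1 − ρ)/2). The sign is reversed: if the better-off patients are in the training arm, their values regress and the bias runs against training.
- False-positive rate: probability that a noncentral t with 2n − 2 degrees of freedom and noncentrality d × √(n/2) exceeds the two-sided 5% limits.

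Example for week-12 values: g = 0.5, ρ = 0.7, n = 40 gives d = 0.35, noncentrality 0.35 × √20 = 1.565, limit 1.991 on 78 df, and a rate of 34.0%.

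**Results** (false-positive rate at n = 20 / 30 / 40 per arm):

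| g | ρ | d, week-12 values | Rate | d, changes | Rate |
|---|---|---|---|---|---|
| 0.3 | 0.5 | 0.15 | 7.5 / 8.8 / 10.2% | −0.15 | 7.5 / 8.8 / 10.2% |
| 0.3 | 0.7 | 0.21 | 9.9 / 12.6 / 15.3% | −0.116 | 6.5 / 7.3 / 8.1% |
| 0.5 | 0.5 | 0.25 | 12.0 / 15.9 / 19.7% | −0.25 | 12.0 / 15.9 / 19.7% |
| 0.5 | 0.7 | 0.35 | 19.0 / 26.6 / 34.0% | −0.194 | 9.2 / 11.4 / 13.7% |

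The ranges are therefore 7.5% to 34.0% for week-12 values and 6.5% to 19.7% for changes.

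**What adjustment would do.** A simulation of 4,000 trials per setting, with g = 0.5, ρ = 0.5 or 0.8, 20 or 30 per arm and no true effect, gave these false-positive rates:

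| Behaviour of the gap | Week-12 t-test | Change t-test | Baseline-adjusted ANCOVA |
|---|---|---|---|
| Shrinks by ρ | 12–33% | 8–15% | 5–6% |
| Fully stable | 34–49% | 5–6% | 8–19% |

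No analysis of these data is safe under both patterns. Adjustment reduces the problem but does not replace random, concealed allocation.

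**The case against.** **Silence is not evidence of non-randomisation.** A reader might infer that this was a non-randomised trial. The text does not support that: the word used for forming the groups neither affirms nor excludes randomisation. This objection stands in full. The supported statement is that no random or concealed allocation is described in the text available for review.

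**The tests are not blind to every imbalance.** A reader might also infer that any selection difference will be taken for a training effect and that the planned tests can neither detect nor remove it. That goes too far. The two-sample and Fisher's tests are not restricted to week 12 and could be run on baseline data, although a non-significant result in small groups would not rule out imbalance. If changes are tested, which the SAP leaves open, a fully stable gap in the outcome itself cancels. A shrinking gap does not, and neither do differences in other prognostic factors that affect how patients change.

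**Steering of patients is conjecture.** The criteria on cooperation and ability to exercise govern entry to both arms, not placement in one of them. The narrow eligibility (age 45–54, HD twice a week, MIP below 70% of predicted, cardiac and pulmonary exclusions) limits some differences. This is fair, and the point does not rest on steering having occurred. Narrow eligibility reduces spread but does not balance the arms. The low-load control may even out expectation, but it has no bearing on who enters which arm.

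**Conclusion.** The point holds as a gap in the plan. The method of allocation is undescribed, the comparison depends on it, and available baseline data go unused in that comparison. It does not hold as a finding that the allocation was non-random or that the arms differ.

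The rates of 7.5% to 34% (week-12 values) and 6.5% to 19.7% (changes, opposite direction) rest on an assumed gap, correlation and arm size, and on the gap shrinking by the correlation. The upper figure for week-12 values needs the extreme of all three. With no systematic gap the rate is 5%. The gap should be closed because every between-group conclusion depends on it and closing it costs little.

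**What to change.** 1. State how the groups were or will be formed: sequence generation, ratio, concealment, and the role that assigns patients. This comes first because much of the protocol is in the past tense, and inserting a randomisation paragraph could put on record a procedure that did not take place. If allocation is still to be done, use a computer-generated 1:1 list in permuted blocks of varying size. It should be held by someone who does not enrol patients and opened only after consent and all baseline measurements.

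2. However the groups were formed, replace the unadjusted between-group test of each continuous outcome with an ANCOVA of the week-12 value adjusted for its own baseline value, transforming skewed outcomes such as IL-6 if needed. This also settles the open choice between end values and changes. Under random allocation it gains precision: residual variance falls to about 1 − ρ², which is 0.75 at ρ = 0.5 and 0.51 at ρ = 0.7.

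3. If allocation was not random, say so, also adjust for prespecified prognostic factors such as baseline MIP, and word the conclusion as an association. Adjustment reduces selection bias but does not remove it.

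Cost: a paragraph in the protocol, a sentence or two in the SAP and, if allocation is still ahead, a computer-generated list and someone outside enrolment to hold it. No extra patients, visits or measurements are needed. If the groups were formed without randomisation, the cost is a more modest conclusion.

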**NCT05241652**

**May 1st, 2022**

**Statistical Analysis Plan (SAP)**

Shapiro-Wilk test will be used to determine the normality of the variables. To compare the two groups, we will use the Unpaired T-test for normally distributed data or the Mann Whitney test for non-normally distributed data. To compare categorical data, we will use the Fisher's test. Paired T-test will be used to compare mean differences before and after intervention for normally distributed data. Wilcoxon's test will be used for non-normally distributed data. The collected data will be analyzed using SPSS version 25.0 for Windows at a statistical significance level (p) of <0.05.

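### The between-group comparison does not adjust for the baseline value collected for every outcome, and does not say whether the week-12 value or the change is tested

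*SAP*

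**What the plan says.** The SAP is one paragraph. For continuous data it compares the groups as follows: "To compare the two groups, we will use the Unpaired T-test for normally distributed data or the Mann Whitney test for non-normally distributed data". The choice between the two tests follows from an earlier sentence: "Shapiro-Wilk test will be used to determine the normality of the variables". For comparisons over time it adds: "Paired T-test will be used to compare mean differences before and after intervention for normally distributed data", with Wilcoxon's test as the non-normal counterpart. It mentions no covariate and no regression or ANCOVA model, and does not say which test decides whether the intervention works.

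The Study Protocol collects each outcome twice. At the start: "We examined the levels of urea, creatinine, and IL-6 (prior to HD) and performed an interview using the KDQOL-SFTM v1.3 questionnaire before the IMT exercise". After 12 weeks: "A re-examination of the urea, creatinine, IL-6 levels, and re-administration of the KDQOL HD-SFTM v1.3 questionnaire was performed at the end". It splits the KDQOL into three summary scores (PCS, MCS, KDCS), so there are six outcomes, each with a baseline.

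On the comparator it says: "The control group received IMT exercise with an intensity of 10% MIP for 12 weeks". On allocation it says only: "Subjects are divided into two groups: control and intervention".

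**The concern.** There are two linked gaps.

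- **No baseline adjustment.** A patient's baseline usually predicts the same patient's week-12 value. An analysis that does not adjust for it leaves that predictable variation in the error term, so the interval for the group difference is usually wider than the collected data require.
- **No named variable.** The same sentence covers a test of week-12 values and a test of changes. These differ in power and respond in opposite directions to a chance difference at baseline. Until the variable is named, the choice can be made after the data are seen.

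The paired tests do not fill either gap. They compare patients with themselves and make no use of the low-intensity control arm, so they cannot separate a training effect from anything else that changes over 12 weeks.

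**Working it through.** **Inputs.** From the documents: six outcomes measured at baseline and week 12, two groups, significance level 0.05. Assumed, because the documents do not give them: two-sided testing, random 1:1 allocation, the correlation r between baseline and week-12 value (0.3, 0.5, 0.7), the number per arm n, and the effect. The plan has no sample size or power figure to reproduce.

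**Step 1: variance of the group difference.** Set the week-12 SD to 1 and let k be the baseline SD as a multiple of it. In large samples:

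- week-12 value: 1
- change: 1 + k² − 2rk, which is 2(1 − r) when k = 1
- ANCOVA: 1 − r²

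| r | Week-12 | Change (k = 1) | ANCOVA |
|---|---|---|---|
| 0.3 | 1 | 1.40 | 0.91 |
| 0.5 | 1 | 1.00 | 0.75 |
| 0.7 | 1 | 0.60 | 0.51 |

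**Step 2: width of the 95% interval.** The width ratio is the square root of the variance ratio.

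- Against week-12: √0.91 = 0.954, √0.75 = 0.866, √0.51 = 0.714, so 5%, 13%, 29% narrower.
- Against change, k = 1: √(0.91/1.40) = 0.806, √(0.75/1.00) = 0.866, √(0.51/0.60) = 0.922, so 19%, 13%, 8% narrower.

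The second line depends on equal SDs:

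- k = 0.8: change variances 1.16, 0.84, 0.52; ANCOVA 11%, 6%, 1% narrower.
- k = 1.2: change variances 1.72, 1.24, 0.76; ANCOVA 27%, 22%, 18% narrower.

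**Step 3: power, for an assumed 0.6 SD effect, n = 30 per arm and k = 1.** The noncentrality for the week-12 test is 0.6 × √(30/2) = 2.32. For the other analyses it is divided by the square root of the variance in Step 1. For ANCOVA that variance is also multiplied by 1 + 1/(2n − 4), and the degrees of freedom are 2n − 3 = 57.

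| r | Week-12 | Change | ANCOVA |
|---|---|---|---|
| 0.3 | 63% | 49% | 66% |
| 0.5 | 63% | 63% | 74% |
| 0.7 | 63% | 84% | 89% |

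**Step 4: where the gain stops.** With the finite-sample factor, ANCOVA is more precise than the week-12 test only when r > 1/√(2n − 3). That is 1/√57 = 0.13 at 30 per arm and 1/√37 = 0.16 at 20 per arm.

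**Step 5: why the unnamed variable matters.** If one arm starts b SD higher by chance (k = 1), the week-12 difference shifts by rb and the change difference by (r − 1)b. For b = 0.3 and r = 0.5 these are +0.15 and −0.15 SD; at r = 0.7 they are +0.21 and −0.09 SD.

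**Step 6: skewed outcomes.** Simulated power for a lognormal outcome left untransformed (skewness 1.75), n = 30 per arm, shift 0.6 SD:

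| r | ANCOVA | Mann-Whitney, week-12 | Mann-Whitney, change |
|---|---|---|---|
| 0.3 | 67% | 79% | 56% |
| 0.5 | 74% | 79% | 71% |
| 0.7 | 87% | 79% | about 89% |

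The false-positive rate of untransformed ANCOVA stayed at 4.5% to 5.1% in simulation. For a skewed outcome (assumed log-SD 0.8) analysed on the log scale, ANCOVA power was 66% to 89%, against 60% for Mann-Whitney on week-12 values and 47% to 81% on change.

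**The case against.** The strongest reply is that nothing in the SAP is wrong: under random allocation both readings are valid, naming the variable would cure the ambiguity, and ANCOVA is then a matter of efficiency. The size of the gain also rests on inputs the documents do not give, and on random allocation, which they do not state. All of this stands, and it limits the point to an improvement. It does not remove it, because the baseline values are already collected and the change costs almost nothing.

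The skew objection also stands in part. For a strongly skewed outcome left untransformed, Mann-Whitney on the week-12 value can beat ANCOVA at r = 0.3 to 0.5. A supportive Mann-Whitney test on change would not protect against this, since at those correlations it is weaker than ANCOVA. The answer is to settle the scale in advance.

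A reader might infer three stronger things that the documents do not support:

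- *That the plan ignores baseline altogether.* If change is tested, baseline enters by subtraction. Only the absence of adjustment is certain.
- *That the false-positive rate is inflated.* It would be about 9% per outcome if both between-group tests were run and the better one reported. The SAP does not say this will be done.
- *That efficacy will rest on the paired tests.* The SAP does not say so; it only leaves their role unstated.

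**Conclusion.** The point holds as a recommended improvement. The between-group comparison does not adjust for an available baseline, and its variable is undefined; neither makes it invalid if allocation was random. On the assumptions above, ANCOVA shortens the interval by 5% to 29% against the week-12 value. Against change the reduction is 8% to 19% with equal SDs, and 1% to 27% if the baseline SD is between 0.8 and 1.2 times the week-12 SD. There is no gain over the week-12 test when r is near 0. The documents give no sample size, SD, effect or correlation, so these figures are illustrations and show no stated number to be wrong. If allocation was not random, the precision argument does not apply as stated: ANCOVA and change scores can then estimate different quantities, and adjusting for baseline alone does not make the comparison causal.

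**What to change.** 1. State in the SAP that for each outcome (urea, creatinine, IL-6, PCS, MCS, KDCS) the deciding analysis is the between-group difference at week 12 from an ANCOVA with group and that outcome's baseline value, reported with its 95% confidence interval.
2. Fix the scale of each outcome before the between-group data are seen. Use the log scale (outcome and baseline) or a rank-based ANCOVA where right skew is expected, such as for IL-6 and any other laboratory value so judged. Do not let the Shapiro-Wilk test choose it.
3. Keep the unpaired t-test or Mann-Whitney test for baseline characteristics and as a supportive comparison of one named variable.
4. Label the paired t-test and Wilcoxon results descriptive, with no efficacy conclusion drawn from them.
5. State how patients were allocated. If not at random, report the ANCOVA result as an adjusted association.

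**Cost.** A few SAP sentences and slightly more analysis work. No new data or patients are needed, and SPSS, which the SAP already names, can run ANCOVA. Log-scale effects are reported as ratios. The gain is small when r is low, and a strongly skewed outcome left untransformed may lose power against Mann-Whitney on the week-12 value at r = 0.3 to 0.5.

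### The SAP applies p<0.05 to every test and names no primary outcome, single contrast, testing order or adjustment across four to six implied outcomes

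*SAP*

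**What the plan says.** The Statistical Analysis Plan is one paragraph. Its last sentence sets the only decision rule: "The collected data will be analyzed using SPSS version 25.0 for Windows at a statistical significance level (p) of <0.05". Two families of tests on the outcome measurements fall under it.

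- Between groups: "To compare the two groups, we will use the Unpaired T-test for normally distributed data or the Mann Whitney test for non-normally distributed data". The sentence does not say which variables are compared, or whether the 12-week value or the change from baseline is used.
- Before/after: "Paired T-test will be used to compare mean differences before and after intervention for normally distributed data", with Wilcoxon's test as the alternative.

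The SAP lists no outcomes, so they have to be taken from the protocol. On laboratory measures it says: "Serum urea and creatinine levels were used to measure kidney function. IL-6 levels were used to measure immune function". On the KDQOL-SF it says: "This questionnaire consists of a physical component summary (PCS), mental component summary (MCS), and kidney disease component summary (KDCS". All are measured at baseline and once more at 12 weeks: "A re-examination of the urea, creatinine, IL-6 levels, and re-administration of the KDQOL HD-SFTM v1.3 questionnaire was performed at the end". The protocol title covers kidney function, immune function and quality of life, and ranks none of them first.

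**The concern.** A reader of the eventual report needs to know which result the trial was set up to deliver. The plan does not say. It has several outcomes, at least two possible between-group contrasts per outcome and a set of before/after tests, all judged at the same level. Nothing prevents a claim of benefit from resting on whichever result falls below 0.05.

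Two things are at stake. First, if one significant between-group outcome is enough, that result is weaker evidence than its nominal level suggests. Second, a significant before/after change in the intervention group could be presented as efficacy. It is not evidence of a difference between groups. The control group also trains, at 10% MIP, so only a between-group contrast speaks to the effect of training intensity.

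**Working it through.** **Reproducing the plan's figure.** The plan states a level of 0.05 and gives no sample size, power or study-wide error rate. For one test with no true effect, the chance of a false difference is 0.05, or 0.025 in the direction of benefit. Nothing else can be reproduced.

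**Inputs from the documents.**
- Level: 0.05 for every test (SAP).
- Groups: two. Post-baseline assessment: one, at 12 weeks (protocol).
- Outcomes: urea and creatinine (2) + IL-6 (1) + PCS, MCS and KDCS (3) = 6; or 2 + 1 + 1 = 4 if the KDQOL-SF is one score.

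**Assumptions, because the documents do not give them.** Tests are two-sided; there is one contrast per outcome; there is no true effect on any outcome; any one significant result counts; and the test statistics are normal with a common correlation ρ, each oriented so that positive means benefit. The choice of t-test or Mann-Whitney after Shapiro-Wilk is not modelled.

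**Formulas.** With c = 1.96 and k tests:
- Independent, either direction: 1 − 0.95^k. Independent, benefit only: 1 − 0.975^k.
- Correlated, either direction: 1 − ∫ φ(u) [Φ((c − √ρ·u)/√(1−ρ)) − Φ((−c − √ρ·u)/√(1−ρ))]^k du. For benefit only, drop the second Φ term.

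**Results: chance of at least one false result.**

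| | ρ = 0 | 0.3 | 0.5 | 0.7 |
|---|---|---|---|---|
| Benefit, six tests | 0.141 | 0.122 | 0.104 | 0.082 |
| Benefit, four tests | 0.096 | 0.087 | 0.078 | 0.065 |
| Either direction, six tests | 0.265 | 0.241 | 0.207 | 0.164 |
| Either direction, four tests | 0.186 | 0.174 | 0.156 | 0.130 |

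The ρ = 0 entries for six tests are 1 − 0.975^6 = 0.141 and 1 − 0.95^6 = 0.265. The 0.7 column is not a floor: at ρ = 0.9, six tests give 0.108 in either direction.

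**The unstated contrast.** Suppose the 12-week value and the change were both tested on one outcome and either counted. With equal variances and baseline-to-week-12 correlation r, the two contrasts correlate at √((1−r)/2), which is 0.59, 0.50 and 0.39 for r = 0.3, 0.5 and 0.7. The chance of a false difference on that single outcome is then 0.088, 0.091 and 0.094.

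**Which contrast is more precise.** The variance of the change, relative to the 12-week value, is 2(1−r): 1.4 at r = 0.3, 1.0 at 0.5 and 0.6 at 0.7. An effect with 80% power on the 12-week value has standardised size 1.960 + 0.842 = 2.802. On the change at r = 0.3 its power is Φ(2.802/√1.4 − 1.960) = Φ(0.408) = 0.66. At r = 0.5 the two are equal, and above 0.5 the change is the more precise.

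**Power at the first Holm step**, for an effect with 80% power at 0.05:
- Five outcomes, 0.05/5 = 0.010: Φ(2.802 − 2.576) = 0.589.
- Six outcomes, 0.05/6 = 0.0083: Φ(2.802 − 2.638) = 0.565.

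**The case against.** The strongest reply is that the SAP sets a level for individual tests. It does not promise a 5% study-wide error rate, and it does not say that an isolated significant result is success. That stands. A reader might infer that the trial's false-positive rate is 13% to 26% rather than 5%. The documents do not support this, because the range needs a success rule, a test count and correlations that they do not state. They establish the silence, not the inflation.

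Other success rules give other numbers. A claim on IL-6 alone carries 5%. A kidney claim that needs both urea and creatinine carries 0.25% (ρ = 0) to 1.65% (ρ = 0.7, as 0.10 − 0.0835). If one component is enough, a kidney claim carries 10% to 8% and a quality-of-life claim 14% to 11%, in either direction.

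It is also fair to say that a result against training would not support a claim of benefit. The false-benefit figures are therefore the more relevant ones, and they are about half the either-direction figures. The comparator halves too, to 2.5%, so the relative excess is similar.

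A reader might also add the before/after tests in both groups, 18 tests in all, and quote 1 − 0.95^18 = 60%. That is not supported either. Those tests share data with the between-group tests, so they are not independent, and a before/after change is not a between-group difference.

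Finally, a primary outcome may be named elsewhere. Part of the SAP file and any registry record were not available here. If a primary is registered, it should be carried into the SAP.

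**Conclusion.** The gap is real and should be fixed. The available text leaves the primary outcome, the between-group contrast, the testing order and any adjustment undefined, while applying p<0.05 to everything.

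The size can only be given conditionally. If any one significant between-group result counted, there were no true effect and the common correlation lay between 0 and 0.7, the chance of at least one false benefit would be about 14% to 8% for six outcomes and 10% to 6.5% for four, against 2.5% for one test. In either direction it would be 26% to 16% and 19% to 13%, against 5%. Stronger correlation lowers these figures (10.8% in either direction for six tests at 0.9). Confidence is high in the gap and lower in any particular percentage, since the success rule and correlations are assumed and the number of outcomes is inferred from the protocol.

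**What to change.** Replace the decision rule in the last SAP sentence with:

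> One primary outcome, named before the data are examined (the registered one if there is one), is compared between groups with one pre-stated contrast at week 12 at two-sided 0.05. The other listed outcomes, with the same contrast, are tested by the Holm procedure at overall two-sided 0.05 only if the primary is significant; otherwise they are exploratory. Within-group before/after tests are descriptive and do not support a claim of benefit.

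List the outcomes in the SAP, and say whether the KDQOL-SF gives three scores or one. The sponsor chooses the contrast. Change from baseline costs precision if the baseline-to-week-12 correlation is below 0.5 (80% power on the 12-week value becomes about 66% at 0.3) and gains it above 0.5. If no single primary is wanted, use Holm over all listed between-group comparisons.

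**Cost.** The change is to SAP wording only, provided the outcome data have not been examined. The primary keeps its full 0.05. The other outcomes give no confirmatory claim if the primary fails. Once they are opened, an effect with 80% power at 0.05 has about 59% at the first Holm step with five others. With no primary and six outcomes, it has about 56% at the first step. The documents give no sample size, so whether the trial can bear this cannot be judged.

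**Timing.** The protocol describes enrolment in the past tense ("This study included patients diagnosed with end-stage CKD who received HD twice a week for more than three months"), while the SAP is in the future tense. If the data have already been examined, naming a primary now does not restore the error rate, and all results should be labelled exploratory.

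This wording does not settle the choice between t-test and Mann-Whitney after a normality test, which is a separate matter.
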